11.3 Planned Analyses

11.3.1 Planned Futility Review

The study will be monitored for futility. The number of treatment failures among subjects eligible for the PP analysis population will be monitored by a statistician independent from the study team. If, at any point in the trial, 30 subjects eligible for the PP analysis population are classified as treatment failures, then the statistician will notify DMID to consider termination of the trial.

The cut-off was chosen because 29 or fewer treatment failures among 257 subjects eligible for the PP analysis population would result in a lower bound of the one-sided 95% Jeffreys confidence interval greater than or equal to 85%. Under the protocol's assumptions of the cure rate, a simulation study based on 50,000 replications found that the operating characteristics (power and type-I error) of this futility review do not vary from those described in section 11.2.

11.4 Final Analysis Plan

A separate statistical analysis plan document will be generated that will contain the details of the analyses. This section outlines the major components of the analyses.

11.4.1 Analysis Populations

Per-Protocol (PP) Population: This analysis population includes enrolled subjects who met all inclusion/exclusion criteria, have *N. gonorrhoeae* isolated on Day 1 culture from the rectum or urogenital site, have an evaluable microbiological outcome status (see section 11.4.3.1), complied with study treatment, did not receive any contraindicated medication or systemic antibiotic other than the study medication for any concomitant infection prior to Visit 2 (Day 5-10), and returned for their Visit 2 (Test of Cure) visit within window.

To be compliant with study treatment, a subject must be able to swallow the pill and not vomit within 1 hour of administration.

For the primary analysis, subjects need only have *N. gonorrhoeae* isolated on Day 1 culture from the rectum or urethra (male) or cervix/vagina (female). For the analysis of secondary objective 1, subjects need to have *N. gonorrhoeae* isolated on Day 1 culture at the particular site being assessed.

In addition, alternate per-protocol analyses which exclude subjects with reported concomitant infection/disease/procedure that may interfere with study product, use of concomitant medications or products that may interfere with study product, significant protocol deviations, and other events that may impact study product

effectiveness or study analyses will be explored. Details will be described in the separate statistical analysis plan.

Microbiological Intent-to-Treat (micro-ITT) Population: This analysis population includes all enrolled subjects who have *N. gonorrhoeae* isolated from the rectum or urogenital site on Day 1 culture.

For the primary analysis, subjects need only have *N. gonorrhoeae* isolated on Day 1 culture from the rectum or urethra (male) or cervix/vagina (female). For the analysis of secondary objective 1, subjects need to have *N. gonorrhoeae* isolated on Day 1 culture at the particular site being assessed.

Intent-to-Treat (ITT) Population: This analysis population includes all enrolled subjects.

Subjects who receive any treatment other than the study medication for their *N. gonorrhoeae* infection will be included in all efficacy analyses as treatment failures.

11.4.2 Baseline Characteristics

Baseline and demographic characteristics will be summarized. For both continuous and categorical variables, appropriate summary statistics will be applied. For continuous variables, descriptive statistics will include the number of non-missing values, mean, standard deviation, median, minimum, and maximum. For categorical variables, descriptive statistics will include counts and percentages per category.

11.4.3 Efficacy and Other Analysis Plan

In this section, the primary and secondary analyses are described. The exploratory analysis will be addressed in the statistical analysis plan and is not described here.

11.4.3.1 Primary Analysis

The primary analysis will test whether the microbiological cure rate of ciprofloxacin in subjects infected with *gyrA* serine 91 genotype *N. gonorrhoeae* is greater than or equal to 95%. The cure rate will be estimated by the proportion of subjects infected with *gyrA* serine 91 genotype *N. gonorrhoeae* with microbiological cure at Visit 2 (Day 5-10).

Microbiological outcome status for the primary analysis is evaluated at Visit 2 (Day 5-10) and is defined as follows:

- Microbiological Cure: *N. gonorrhoeae* not detectable by culture from all anatomical sites that had detectable *N. gonorrhoeae* at Visit 1.

-
- Microbiological Failure: *N. gonorrhoeae* detectable by culture from at least one anatomical site that had detectable *N. gonorrhoeae* at Visit 1.
 - Non-evaluable: At least one of the following: Subject did not return for Visit 2 (Day 5-10), or culture results at Visit 2 (Day 5-10) were not available for any reason, or subject could not be evaluated for microbiological outcome status for any other reason.

For the PP analysis population, subjects with non-evaluable outcome status will be excluded from the analysis. For the micro-ITT and ITT analysis populations, subjects with non-evaluable outcome status will be included in analyses and classified as treatment failures. Subjects who discontinued early from the study due to a lack of treatment effect are included in all analysis populations as treatment failures.

The test will be performed by calculating the one-sided 95% modified Jeffreys confidence interval and comparing it to the value 0.95. The modification to the Jeffreys confidence interval was introduced in Brown, Cai, and DasGupta [18]. The lower bound of the confidence interval will be calculated as follows:

If the number of cures, denoted X , is less than the number of subjects included in the analysis, denoted N , then the lower bound of the one-sided 95% confidence interval is:

$$B(0.95; X + 0.5; N - X + 0.5)$$

where $B(\alpha; m_1; m_2)$ denotes the α quantile of a Beta(m_1, m_2) distribution.

If the number of cures is equal to the number of subjects included in the analysis, denoted N , then the lower bound of the one-sided 95% confidence interval is:

$$(0.05)^{1/N}$$

The primary analysis will be performed in the PP analysis population. Secondary analyses of the primary outcome measure will be performed in the micro-ITT and ITT analysis populations. Sensitivity analyses may be performed to assess the impact of the choice of confidence interval. These analyses will be specified in the statistical analysis plan.

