11 STATISTICAL CONSIDERATIONS

11.1 Study Hypotheses

The primary objective of the study is to clinically validate a *gyrA* assay used to determine ciprofloxacin susceptibility in the treatment of uncomplicated gonococcal infection by assessing the efficacy of ciprofloxacin for treatment of uncomplicated *N. gonorrhoeae* infections with serine 91 *gyrA* genotype as identified by the *gyrA* assay.

The study is designed to test the following hypothesis in the primary efficacy analysis conducted in the per-protocol (PP) analysis population:

Null hypothesis: The proportion of ciprofloxacin-susceptible (as identified by the *gyrA* assay) *N. gonorrhoeae*-infected subjects with microbiological cure 5-10 days after receiving ciprofloxacin is less than 0.95.

Alternative hypothesis: The proportion of ciprofloxacin-susceptible (as identified by the *gyrA* assay) *N. gonorrhoeae*-infected subjects with microbiological cure 5-10 days after receiving ciprofloxacin is at least 0.95.

The cut-off of 0.95 was chosen based on the CDC criteria for treatments of uncomplicated *N. gonorrhoeae* infections. The criterion for recommended treatments is a cure rate of greater than 95% with a lower bound of the 95% confidence interval of at least 95%. The criterion for alternative treatments is a cure rate of greater than 95% with a lower bound of the 95% confidence interval of at least 90%.

[figure not shown]

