11.2 Sample Size Considerations

The primary analysis will compute the proportion of ciprofloxacin-susceptible *N. gonorrhoeae*-infected subjects with microbiological cure 5-10 days after receiving ciprofloxacin in the PP analysis population. The confidence interval for the microbiological cure proportion will be computed using a one-sided modified Jeffreys interval using a significance level of 0.05. Power calculations were performed via a simulation study based on 10,000 replications assuming a 98% microbiological cure rate.

Figure 11.2 below presents the power available to test that the microbiological cure rate is at least 95% (i.e., lower bound of the one-sided confidence interval is at least 95%) across a range of evaluable sample sizes. Here, evaluable denotes eligible for the PP analysis population. The power reaches 80% at a sample size of 195 evaluable subjects; however, since the power curve is not monotonic, sample sizes directly on either side of 195 are below 80%. Since the exact number of evaluable subjects at the end of the study is difficult to predict, an evaluable target of 257 subjects is chosen to ensure at least 80% even if the exact number of evaluable subjects at the end of the study differs

slightly from 257. With a target of 257, the power available is approximately 85% and we can fall at most 10 subjects short (sample size of 247 evaluable subjects) and still ensure 80% power. Any sample size greater than 257 will ensure at least 80% power.

Figure 11.2: Power Available to Test That the Microbiological Cure Rate Is at Least 95%

To calculate the number of subjects required to enroll to reach 257 subjects in the PP analysis population, the following assumptions are made:

- 25% of enrolled subjects will be culture negative at baseline.
- 10% of subjects will be excluded from the PP analysis population (reasons for exclusion are stated in section 11.4.1)

Under these assumptions, enrolling 381 subjects will provide 257 subjects in the PP analysis population. Since the proportion of subjects who will be culture negative at baseline can vary depending on a number of factors, 25% is a rough estimate. The exact number of subjects needed to provide 257 subjects in the PP analysis population may vary from 381, so 381 is an approximate enrollment target.

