6.1.1. Pseudo Code

The following SAS® pseudo code will be used to calculate the following:

Lower bound of the one-sided 95% Jeffreys CI for proportions/percentages if the number of cures is less than the number of subjects included in the analysis:

```
proc freq;  
    tables cure / alpha=0.1 binomial(jeffreys);  
run;
```

Lower bound of the one-sided 95% Jeffreys CI for proportions/percentages if the number of cures is equal to the number of subjects (n) included in the analysis:

```
CI_Lower = 0.05** (1/n);
```

95% Wilson CI for proportions/percentages:

```
proc freq;  
    Table treatment*analysisvariable / alpha=0.1 binomial(wilson);  
    ods output binomialcls=outputdsn;  
run;
```

95% Exact Blaker CI for proportions/percentages:

```
proc freq;  
    Table treatment*analysisvariable / alpha=0.1 binomial(blaker);  
    ods output binomialcls=outputdsn;  
run;
```

95% Agresti-Coull CI for proportions/percentages:

```
proc freq;  
    Table treatment*analysisvariable / alpha=0.1 binomial(AC);  
    ods output binomialcls=outputdsn;  
run;
```

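### The protocol's formula for the primary lower confidence bound takes the 0.95 Beta quantile, which is the upper bound; as written, the primary test passes 94% of the time at a true cure rate of 95%

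*Protocol*

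**What the plan says.** Protocol 11.4.3.1 tests the primary hypothesis by comparing a one-sided 95% modified Jeffreys limit with 0.95. It introduces the formulas with "The lower bound of the confidence interval will be calculated as follows". When the number of cures X is below the number analysed N, the limit is "B(0.95; X + 0.5; N - X + 0.5"), where B with first argument alpha is the alpha "quantile of a Beta(m_1, m_2) distribution". When X = N, the limit is 0.05^(1/N).

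Protocol 11.2 describes a "one-sided modified Jeffreys interval using a significance level of 0.05" and counts success when the "lower bound of the one-sided confidence interval is at least 95"%. Under the null hypothesis in Protocol 11.1, the proportion with "microbiological cure 5-10 days after receiving ciprofloxacin is less than 0.95". The same section ties the threshold to the CDC standard, with 95% as the required limit: "The criterion for recommended treatments is a cure rate of greater than 95% with a lower bound of the 95% confidence interval of at least" that value.

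SAP 8.1 keeps the same test and sends the reader to SAP 6.1.1 for code. For X < N that code is "tables cure / alpha=0.1 binomial(jeffreys"), and for X = N it is 0.05^(1/n). SAP section 15 reports no changes to the planned analyses.

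**The concern.** B is defined by its quantile level, so the 0.95 in the formula cannot be read as a confidence level or an upper-tail probability. Taken literally, the X < N line is the upper one-sided 95% limit, labelled as the lower one.

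This line is the primary decision rule. Requiring an upper limit of at least 0.95 asks only that the data do not rule out a 95% cure rate. It does not show that the cure rate reaches 95%, which is what the hypothesis and the CDC criterion require. Protocol 11.4.3.2 sends the by-site analyses of secondary objective 1 back to the same section, so they inherit the line.

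**Working it through.** **Inputs.** N = 257 evaluable, assumed cure rate 0.98, one-sided level 0.05 and power of about 85% (Protocol 11.2); null boundary 0.95 (Protocol 11.1); futility cut-off of 29 failures giving a lower limit of at least 85% (Protocol 11.3.1); the two formulas (Protocol 11.4.3.1).

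**Method.** For f = N − X failures, the limit is the q quantile of Beta(X + 0.5, N − X + 0.5) when X < N, and 0.05^(1/N) when X = N. Success means a limit of at least 0.95. Probabilities are exact binomial sums over the successful values of X. Each calculation was run with q = 0.05 (the true lower limit) and q = 0.95 (as printed).

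**1. Reproducing the plan's own figures.**

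| Plan's statement | q = 0.05 | q = 0.95 (printed) |
|---|---|---|
| Power about 85% at N = 257 | 85.4% | above 99.99% |
| Power reaches 80% at N = 195, below 80% on either side | 80.2%; 65.2% at 194 and 79.9% at 196 | essentially 100% at all three |
| At least 80% power at N = 247 | 87.5% | essentially 100% |
| 29 failures of 257 give a limit of at least 0.85 | 0.8515 (30 failures: 0.8472) | 0.9164; stays at or above 0.85 up to 48 failures |

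Only the 0.05 quantile reproduces the design. A two-sided 95% version (q = 0.025) gives 74.3% power at 257, so it was not the basis either.

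**2. Consistency with the X = N formula.** With no failures the limit is 0.05^(1/257) = 0.9884. The printed X < N formula gives 0.9993 with one failure and 0.9911 with five, so the limit would rise when failures occur. With q = 0.05, one failure gives 0.9849, below 0.9884 as it should be.

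**3. Success boundary at N = 257.**

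| Failures | Observed cure | 0.05 quantile | 0.95 quantile |
|---|---|---|---|
| 7 | 97.3% | 0.9519 | 0.9858 |
| 8 | 96.9% | 0.9470 | 0.9830 |
| 18 | 93.0% | 0.9002 | 0.9527 |
| 19 | 92.6% | 0.8957 | 0.9494 |

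The intended rule needs at least 250 cures (at most 7 failures). The printed rule needs only 239 (at most 18). At 18 failures the supposed lower limit, 0.9527, lies above the estimate itself, 239/257 = 0.9300.

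**4. Probability of declaring success, N = 257.**

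| True cure rate | q = 0.05: P(X ≥ 250) | q = 0.95: P(X ≥ 239) |
|---|---|---|
| 0.98 | 85.4% | above 99.99% |
| 0.95 | 5.4% | 94.1% |
| 0.93 | 0.2% | 56.3% |
| 0.92 | 0.04% | 32.7% |
| 0.90 | below 0.01% | 6.2% |

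**5. The SAP code.** With alpha = 0.1 the Jeffreys limits are the 0.05 and 0.95 quantiles, so the lower limit is the 0.05 quantile. The SAP code and the protocol formula therefore define different primary tests. They disagree for 8 to 18 failures.

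**The case against.** The strongest reply is that this is a one-digit slip with no practical effect. Protocol 11.4 leaves the analysis details to the SAP, and SAP 8.1 points to code that takes the correct quantile. The protocol repeatedly calls the quantity a lower bound, states a 0.05 level, and has an X = N case, a power figure and a futility cut-off that all fit the lower tail. An analyst would notice a lower limit above the point estimate. The pass probabilities in the q = 0.95 column therefore describe a test that the SAP code would not run. Also, the null hypothesis is composite, and the inflation is extreme only near its boundary: at a true rate of 0.90 even the printed rule passes only 6.2% of the time.

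Most of this stands. The intent is clear, the sample size and futility rule were built on the right quantile, and running the SAP code gives the intended test. It does not remove the discrepancy. The SAP presents itself as describing and expanding the protocol's statistics, gives no closed form in section 8.1, and acknowledges no departure. The only explicit formula for X < N in either document is the wrong one. Protocol section 16 says both documents will be posted publicly, so a reader applying the protocol could reach the opposite conclusion from the study report.

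**Conclusion.** The protocol formula is wrong as written and must be corrected. It gives the upper one-sided 95% limit in place of the lower. If followed literally at N = 257, it raises the allowable failures from 7 to 18 and the chance of passing at a true cure rate of 0.95 from 5.4% to 94.1%.

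These figures assume exactly 257 evaluable subjects, independent binomial outcomes and literal use of the printed line. They do not show that the SAP code, the sample size, the power or the futility rule is wrong; all of those agree with the 0.05 quantile. The importance comes from the line being the primary decision rule, on which the two documents conflict without saying so.

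The corrected rule still has an exact error rate of 5.4% at N = 257, slightly above 5%, because the Jeffreys interval is not strictly conservative. That is a separate and smaller matter.

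**What to change.** - In Protocol 11.4.3.1, change the first argument of B from 0.95 to 0.05, so that the X < N limit reads B(0.05; X + 0.5; N − X + 0.5). Leave the X = N formula as it is.
- In SAP 8.1, state the same closed form beside the reference to the code, so that text and code can be checked against each other. This is helpful rather than essential, since the code in 6.1.1 is already right.
- In SAP section 15, record that the protocol formula was corrected and that the analysis uses the 0.05 quantile.

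The cost is one corrected number in the protocol and a line or two in the SAP. Design, sample size, data collection and SAP code do not change. The correction should be made before the primary analysis is run.

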11.4.3.2 Secondary Analyses

The analysis of the efficacy of by anatomic site (secondary objective 1) will proceed as described in section 11.4.3.1 where the modification to

the definition of microbiological outcome status is provided below. Summaries of the cure rate estimate and associated confidence interval and hypothesis test will be generated for each individual anatomic site.

For the analysis of secondary objective 1, microbiological outcome status at each anatomical site is evaluated at Visit 2 (Day 5-10) and is defined for a particular anatomical site as follows:

- Microbiological Cure: *N. gonorrhoeae* not detectable by culture at the particular anatomical site that had detectable *N. gonorrhoeae* at Visit 1.
- Microbiological Failure: *N. gonorrhoeae* detectable by culture at the particular anatomical site that had detectable *N. gonorrhoeae* at Visit 1.
- Non-evaluable: At least one of the following: Subject did not return for Visit 2 (Day 5-10), or culture results at Visit 2 (Day 5-10) were not available for any reason, or subject could not be evaluated for microbiological outcome status for any other reason.

For the analysis of the sensitivity of the *gyrA* assay for the detection of ciprofloxacin-susceptible *N. gonorrhoeae* infections (secondary objective 2), the sensitivity will be estimated by calculating the proportion of enrolled subjects who have ciprofloxacin-susceptible *N. gonorrhoeae* as identified by culture-based antimicrobial susceptibility testing at Visit 1. The proportion of enrolled subjects who do not have ciprofloxacin-susceptible *N. gonorrhoeae* will also be estimated. This analysis will be performed in the micro-ITT analysis population. Secondary and sensitivity analyses, which will assess the impact of analysis population and missing antimicrobial susceptibility testing, may be performed. These analyses will be specified in the separate statistical analysis plan document.

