3.2.2 Secondary Outcome Measures

- 1) The proportion of subjects infected with *gyrA* serine 91 genotype *N. gonorrhoeae* with microbiological cure at each anatomic site (throat, rectum, male or female urogenital tract) at Visit 2 (Day 5-10)
- 2) The proportion of subjects infected with *gyrA* serine 91 genotype *N. gonorrhoeae* identified by *gyrA* gene PCR who have ciprofloxacin-susceptible *N. gonorrhoeae* as identified by culture-based antimicrobial susceptibility testing at Visit 1 (Day 1)

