5 STUDY ENROLLMENT AND WITHDRAWAL

5.1 Subject Inclusion Criteria

Subjects must meet all of the inclusion criteria in order to be eligible to participate in the study. Subjects who present with a new *N. gonorrhoeae* infection may be rescreened for eligibility. No exemptions are granted on Subject Inclusion/Exclusion Criteria in DMID-sponsored studies.

1. Willing and able to give voluntary written informed consent before any study related procedure is performed.
2. 18 years or older on the day of enrollment.
3. Untreated *gyrA* serine 91 genotype *N. gonorrhoeae* of the rectum, or male or female urogenital tract*, as determined by the *gyrA* test assay on a specimen collected within 30 days of enrollment.
*Subjects must have *gyrA* serine 91 genotype detected for *N. gonorrhoeae* from at least one non-pharyngeal site.
4. Willing to abstain from sexual intercourse or use condoms during any sexual contact until the Test of Cure Visit (Visit 2, Day 5-10) is complete.
5. Women of childbearing potential* must have no vaginal intercourse 14 days before enrollment or use an effective birth control method ** for 30 days before enrollment and agree to continue through visit 2.
*A woman is considered of childbearing potential unless post-menopausal (>2 years) or surgically sterilized (tubal ligation >1 year, bilateral oophorectomy, or hysterectomy).
**Acceptable birth control methods for the purposes of this study may include abstinence from intercourse with a male partner, monogamous relationship with vasectomized partner, male condoms with the use of applied spermicide, intrauterine devices, and licensed hormonal methods. A highly effective method of contraception is defined as one that results in a low failure rate (i.e., less than 1% per year) when used consistently and correctly.
6. Able to swallow pills.
7. Willing to comply with protocol requirements, including availability for follow-up for the duration of the study.
8. Agree to avoid systemic or intravaginal antibiotics* with activity against *N. gonorrhoeae* from enrollment through Visit 2 (Day 5-10). *Topical and intravaginal antifungals are permitted.
9. Agree to avoid magnesium/aluminum antacids, sucralfate, didanosine, or highly buffered drugs, up to 2 hours after receipt of study drug.

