5.2 Subject Exclusion Criteria

Subjects meeting any of the following criteria at enrollment will be excluded from the study:

1. Known renal insufficiency from clinical history.
2. Use of systemic or intravaginal antibiotics* with potential activity against *N. gonorrhoeae* within 30 days prior to study drug administration. *Topical and intravaginal antifungals are permitted.
3. Use of systemic corticosteroid drugs or other immunosuppressive therapy within 30 days prior to enrollment.
4. Receipt or planned receipt of an investigational product in a clinical trial within 30 days prior to or 7 days after treatment administration.
5. Pregnant or breastfeeding.
6. Clinical diagnosis of pelvic inflammatory disease or genital ulcer.
7. Confirmed or suspected complicated or systemic gonococcal infection, such as abdominal pain, testicular pain, epididymitis, orchitis, arthritis, or endocarditis.
8. Receipt of magnesium/aluminum antacids, sucralfate, didanosine, or highly buffered drugs, within 6 hours before receipt of study drug.
9. Mutant *N. gonorrhoeae gyrA* serine 91 genotype from any anatomic site, as determined by the *gyrA* test assay on a specimen collected within 30 days of enrollment.
10. Known allergy or history of adverse reaction to ciprofloxacin.
11. Known allergy to quinolones.
12. Previous enrollment in this study.
13. Medical condition or other factor that in the judgment of the investigator might affect ability to comply with procedures.

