3.3.3. Sensitivity of the *gyrA* assay

For the analysis of the sensitivity of the *gyrA* assay for the detection of ciprofloxacin-susceptible *N. gonorrhoeae* infections (secondary objective 2), two measures will be estimated. First, the sensitivity of the assay will be estimated using the following (overall and separately for each anatomical site):

True Positives (TP): the number wild type *gyrA* infections that are ciprofloxacin-susceptible *N. gonorrhoeae* as identified by culture-based antimicrobial susceptibility testing at Visit 1.

False Negatives (FN): the number of non-wild type *gyrA* infections that are ciprofloxacin-susceptible *N. gonorrhoeae* as identified by culture-based antimicrobial susceptibility testing at Visit 1.

$$\text{Sensitivity} = \text{TP} / (\text{TP} + \text{FN})$$

Given the design of the study, the estimate of sensitivity may be biased because subjects with no wild type infections are not enrolled and thus their samples are not tested for culture-based susceptibility testing. To supplement the estimates of sensitivity, the assay's positive predictive value (PPV) will also be estimated. PPV is calculated using the following (overall and separately for each anatomical site):

True Positives (TP): the number wild type *gyrA* infections that are ciprofloxacin-susceptible *N. gonorrhoeae* as identified by culture-based antimicrobial susceptibility testing at Visit 1.

False Positives (FP): the number of wild type *gyrA* infections that are not ciprofloxacin-susceptible *N. gonorrhoeae* as identified by culture-based antimicrobial susceptibility testing at Visit 1.

$$\text{PPV} = \text{TP} / (\text{TP} + \text{FP}).$$

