8.2. Secondary Efficacy Analyses

The analysis of the first secondary endpoint will proceed using the same methods as the primary efficacy analysis using the anatomical site-specific definition of microbiological outcome status (see Section 3.3.2). Summaries of the cure rate and associated confidence interval will be generated for each individual anatomical site and analysis population (Table 11).

For the analysis of the second secondary endpoint, the sensitivity and positive predictive value of the *gyrA* assay will be estimated as described in Section 3.3.3. This analysis will be performed by anatomic sites in the ITT analysis population. See Table 12.

The summaries of *N. gonorrhoeae* culture results, NAAT testing results and *gyrA* assay results will be presented by each anatomical site and visit (Table 13, Table 14, and Table 15). Listing 5 and Listing 6 provide a complete listing of individual microbiological results.

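### Secondary objective 2 is called sensitivity, but the protocol's formula is a positive predictive value, and the enrolment rule biases the SAP's substitute upward

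*Protocol*

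**What the plan says.** **Objective and outcome measure.** Both documents name secondary objective 2 as the sensitivity of the assay (section 3.1.2 in each). The matching outcome measure (section 3.2.2 in each) does not use that word. It takes subjects identified as wild type by PCR and asks what proportion are susceptible on culture-based testing at Visit 1.

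**Protocol analysis (11.4.3.2).** The text states that "the sensitivity will be estimated by calculating the proportion of enrolled subjects who have ciprofloxacin-susceptible" infection at Visit 1. On the population it adds: "This analysis will be performed in the micro-ITT analysis population".

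**Who is enrolled.** Under Protocol 5.1, criterion 3: "Subjects must have *gyrA* serine 91 genotype detected for *N. gonorrhoeae* from at least one non-pharyngeal site". Protocol 5.2, criterion 9 excludes: "Mutant *N. gonorrhoeae gyrA* serine 91 genotype from any anatomic site, as determined by the *gyrA* test assay" on a specimen from the 30 days before enrolment.

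**SAP analysis.** Section 3.3.3 defines sensitivity as TP/(TP+FN), where FN are non-wild-type infections that are susceptible on culture. It warns that "the estimate of sensitivity may be biased because subjects with no wild type infections are not enrolled", and adds PPV = TP/(TP+FP) as a supplement. Section 8.2 says: "This analysis will be performed by anatomic sites in the ITT analysis population". Section 6.5 limits the analysis to specimens with determinate results on both tests. Section 15 declares no change in the planned analyses.

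**The concern.** Sensitivity is the share of truly susceptible infections that the assay calls wild type. It needs a sample of susceptible infections that were not chosen by the assay's own answer. Here the assay decides entry, so the sample supports a PPV and does not directly support a sensitivity.

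The two documents meet this problem in different ways. The protocol computes a PPV and calls it sensitivity. The SAP uses the textbook formula on a sample already depleted of the false negatives that the formula has to count. The stated purpose in Protocol 11.1 is to validate the assay clinically. An accuracy figure reported under the wrong name, or with an upward bias of unstated direction, could therefore be carried forward as a property of the test.

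**Working it through.** **Inputs from the documents**
- Enrolment 381, PP target 257, 25% culture negative at baseline, 10% other PP exclusions (Protocol 11.2).
- Background sensitivity 93% and specificity 100% against standard susceptibility testing (Protocol 2.1).
- 13.5% of isolates with MIC at or above 0.125 µg/mL (Protocol 2.2). The SAP cut-off for susceptible is below 1 µg/mL (3.3.8), so the susceptible share is at least 86.5% on that basis.

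The documents give no expected value, precision or sample size for secondary objective 2. The enrolment figure reproduces: 257/(0.75 × 0.90) = 380.7, so 381. Expected culture-positive subjects: 381 × 0.75 = 285.75, about 286.

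**Step 1. What the protocol ratio estimates.** With wild type as the positive result, the denominator is assay-positive subjects and the numerator is those who are susceptible:

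PPV = Se × prev / [Se × prev + (1 − Sp) × (1 − prev)]

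At Se = 93%, Sp = 100% and prev = 86.5% the ratio is 100%, although the sensitivity is 93%. With assumed lower specificities it still hardly responds to sensitivity:

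| Susceptible | Specificity | Se 70% | Se 99% |
|---|---|---|---|
| 86.5% | 95% | 98.9% | 99.2% |
| 86.5% | 90% | 97.8% | 98.4% |
| 75% | 90% | 95.5% | 96.7% |

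An assay with no information (Se = Sp = 50%) would give 86.5%.

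**Step 2. How a false negative can reach the SAP formula.** Criteria 3 and 9 remove infections called mutant at screening. Three routes remain:
- the Visit 1 assay disagrees with screening;
- a site is first swabbed at Visit 1 because clinically indicated (Protocol 7.1, Note 1);
- an ineligible subject is enrolled.

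**Step 3. Size of the bias.** Take 286 enrolled susceptible infections, assuming one per culture-positive subject, all susceptible and all with paired results. Let q be the chance that a susceptible infection read as wild type at screening is read as mutant at Visit 1. The SAP estimate then has expectation 1 − q.

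- *Independent re-test errors:* q = 7%. Expected FN = 286 × 0.07 = 20.0, and the estimate is 93%. There is no bias.
- *Intermediate (assumed):* q = 5%, 2% and 1% give 95%, 98% and 99%, with 14.3, 5.7 and 2.9 FN.
- *Fully repeated misreads:* q = 0. The estimate is 286/286 = 100%. By the plan's rule for all successes, the one-sided 95% lower bound is 0.05^(1/286) = 0.9896, or 99.0%. Susceptible infections lost at screening: 286/0.93 − 286 = 21.5, about 22. If true sensitivity were 99% or 80% (assumed), about 3 or 72 would be lost (286/0.99 − 286 = 2.9; 286/0.80 − 286 = 71.5).

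**Step 4. Formula and population side by side.** The protocol has susceptible over enrolled in micro-ITT. The SAP has TP/(TP+FN) in ITT. Both elements differ, and SAP section 15 records neither.

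**The case against.** The SAP has gone a good way to meet this. It names the design cause, warns of bias, adds PPV with an explicit formula, and lays out the full cross-table in Table 12, where a nearly empty false-negative cell would be visible. The population difference is small in practice. Susceptibility testing needs a positive culture and section 6.5 requires paired results, so ITT adds to the protocol's micro-ITT little beyond subjects who are culture positive only at the pharynx. Protocol 11.4.3.2 also lets the SAP examine the effect of analysis population. The estimate is secondary and has no threshold or stated power.

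All of that stands, and it limits the weight of the point. It does not remove it. The caveat gives no direction. It also speaks only of subjects with no wild-type infection, whereas criterion 9 excludes a subject with a mutant result at any site. PPV remains a supplement to an estimate still called sensitivity.

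A reader might infer more than the documents support:
- *That false negatives cannot occur.* They can, by the three routes above. They would be zero by definition only under the SAP's micro-ITT, which requires wild type. The protocol's micro-ITT has no such condition, and the SAP runs this analysis in ITT.
- *That about 100% would be reported whatever the true sensitivity.* That holds only if misreads repeat. With independent errors the bias vanishes.
- *That the protocol ratio is near 100% by construction.* Each non-susceptible isolate lowers it. Its fault is that it estimates something else.

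**Conclusion.** The point holds. The protocol's formula for objective 2 is a PPV under the name of sensitivity, and the outcome measures in both documents already describe that PPV. The SAP's TP/(TP+FN) is biased upward to the extent that assay misreads repeat between screening and Visit 1. At 93% true sensitivity the expected estimate lies between 93% and 100%. At the top of that range the one-sided lower bound would be 99.0%.

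The range rests on 286 susceptible infections with paired results and on the quoted 93%; the documents do not say how repeatable misreads are. An interval for this estimate is itself an inference from the general rule in SAP 6.1, since neither SAP 3.3.3 nor Table 12 specifies one. The change of formula and population should have been declared in SAP section 15. The primary analysis, sample size and futility rule are not affected.

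**What to change.** 1. Rename objective 2 as the positive predictive value of the *gyrA* assay in Protocol 3.1.2 and 11.4.3.2 and in SAP 3.1.2, 3.3.3 and 8.2. The outcome measures in section 3.2.2 of both documents need no change.
2. Make PPV the reported estimate with Table 12, whose shell now shows only counts and percentages.
3. Drop the sensitivity estimate, or label it: *Visit 1 gyrA wild-type proportion among culture-susceptible infections in subjects enrolled on a wild-type screening result; not assay sensitivity, biased upward to the extent that misreads repeat*. A label that mentions only re-test agreement would be wrong, because some sites may be assayed for the first time at Visit 1.
4. State one population in both documents: Visit 1 specimens of enrolled subjects with paired determinate *gyrA* and susceptibility results, as SAP 6.5 already has it.
5. Record the change of formula and population in SAP section 15.

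**Cost.** Wording amendments, a row in one table, and ethics approval of the protocol amendment before use (Protocol 14.2). No new data are needed. The trial gives up its claim to a sensitivity, which could be estimated properly only with culture-based testing of patients called mutant at screening.
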